3.3.1. Primary Efficacy – Bleed Rate on Prophylaxis Compared to On-Demand

Only OD subjects will be included in this analysis.

3.3.1.1. Variable Definition

To assess the efficacy of routine prophylaxis and on-demand treatment, the annualized bleed rate (ABR) or number of bleeds per year, will be derived for each subject for each treatment regimen by using the following formula:

ABR = number of bleeds/(Days on treatment regimen/365.25)

The number of bleeds for the ABR calculation includes all bleeds requiring treatment with a FVIII replacement product during the time on treatment. For segment 1 (on-demand treatment), days on treatment regimen for this calculation is defined as (date of visit 11 – date of visit 2) +1. For segment 2 (prophylaxis), days on treatment regimen for this calculation is defined as (date of visit 19 – date of visit 11). If a subject does not complete a study segment, the days on treatment ends at the last study visit. The ABR will be calculated 3 ways: 1) including all data from the ITT population (all OD subjects), 2) including all data from the PR-OD population and 3) including all data from the PR-OD population excluding the first month of segment 2 as a washout period (and allowing for an analysis of the sensitivity of ABRs to previous therapy).

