Target joint	A major joint (eg, hip, elbow, shoulder, knee, ankle) into which repeated bleeding occurs (frequency of 3 or more bleeding episodes over 6 months), and/or clinical signs and/or symptoms of underlying target joint damage (synovitis, persistent swelling, effusion, limitation of range of motion, eg any objective limitation or joint held in flexion or "frozen").
Test article	Any drug, comparator, placebo, nutritional product, dietary supplement, herbal product, vaccine, biologic product, or device used in the Sponsor's studies. For test article accountability, this term applies to such articles when they are required by the protocol and supplied (shipped) by the Sponsor (including diluents such as sterile water for injection).
Time on study	Time from signing the informed consent/assent to last study contact reported for study participation.
TN8.2	The affinity ligand used during the moroctocog alfa (AF-CC) purification process.

Term	Definition
Treatment phase of the study	Period of time during which subject receives study drug. The period starts at study visit 2 (day 1) and ends at the Final Study Visit (visit 15, month 18 or visit 19, month 24, depending on the cohort into which the subject is enrolled).
Washout	The time between the last dose of FVIII replacement product or blood product (eg, fresh frozen plasma, cryoprecipitate, blood) and the collection of FVIII activity or other laboratory information. For this study, the minimal washout time is 72 hours. The intent of the washout is to allow complete clearance of previous FVIII replacement therapy from the blood.

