To achieve its objectives, this study evaluates moroctocog alfa (AF-CC) in the context of two settings. A cohort of subjects was enrolled who practiced on-demand therapy for a 6-month period during segment 1, then switched to prophylaxis with moroctocog alfa (AF-CC) for a 12-month period in segment 2, practicing a protocol-defined regimen (25 ±5 IU/kg, administered every other day). This regimen has been well characterized and has demonstrated efficacy relative to on-demand therapy, although in a different patient population. A second cohort, comprising all other subjects, will practice a single moroctocog alfa (AF-CC) treatment modality, prophylaxis, during this study, but treatment

will include practice of each of the two protocol-defined regimens; these subjects will follow one of the two randomly assigned protocol-defined regimens for a 12-month period (segment 1), and then will crossover to the other regimen for a second 12-month treatment period (segment 2). Study subjects will be hereafter referred to by their segment 1 treatment modality: on-demand (OD) subjects and routine prophylaxis (RP) subjects. This study design allows direct evaluation of moroctocog alfa (AF-CC) in the prophylaxis and on-demand settings, as well as a direct comparison between 2 different moroctocog alfa (AF-CC) prophylaxis-dosing schedules. The duration of moroctocog alfa (AF-CC) treatment in this study (18 - 24 months depending on the cohort) ensures that sufficient experience with moroctocog alfa (AF-CC) is obtained.

Pharmacokinetic assessment of FVIII:C after FVIII therapy has shown lower FVIII:C recovery, in young children. For moroctocog alfa, this has also been observed: a mean incremental recovery of  $1.5 \pm 0.6$  IU/dL per IU/kg, in 59 children with median age  $10 \pm 8.3$  months was reported compared with mean incremental recovery of  $2.4 \pm 0.4$  IU/dL per IU/kg in 101 patients with a median age of  $26 \pm 12$  years. Younger patients also have higher clearance, when adjusted for body size and shorter half-lives compared with older children and adults. A secondary objective of this study is to continue to characterize the pharmacokinetics of moroctocog alfa (AF-CC) in pediatric patients. To achieve this objective, a subset of enrolled subjects will participate in a pharmacokinetic assessment conducted at the start of the study.

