#### 14. CONCOMITANT TREATMENT

#### 14.1. Prohibited

Concomitant treatment with FVIII concentrates, other than moroctocog alfa (AF-CC) study drug, is not allowed during the treatment phase of this study: the treatment phase starts at visit 2 (day 1) and ends at the Final Study Visit (ie, visit 19, month 24 for RP subjects). After completion of the treatment phase of this study, subjects may use the FVIII concentrate of their choice and should not use study drug.

Subjects should not receive drugs with antiplatelet effects (eg, aspirin) or use certain NSAIDs to a degree that, in the opinion of the investigator or Sponsor's clinician, affects the hemostatic function of the subject, and/or affects the subject's FVIII therapy.

The regular use of immunomodulating drugs (eg, IVIG, routine systemic corticosteroids) is prohibited.

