APPENDIX C: CHANGES IN THE PLANNED ANALYSES FROM INTERIM	
CSRS	33

OVERVIEW AND SUMMARY OF CHANGES TO PLANNED ANALYSES FOR THE FINAL CSR

OVERVIEW

Version 5.0 of this statistical analysis plan (SAP) incorporates updates resulting from Protocol Amendments 5 (A5) through the current Amendment 10 (A10) (including a 2017 Protocol Administrative Change Letter). Text taken directly from the protocol appears in italics. Major updates include a shortened duration for Segment 1 for the on-demand (OD) cohort to 6 months duration from 12 months (Amendment 7 [A7]), removal of incremental recovery assessment at visit 7 and consequently the analysis of k-value (incremental) recovery over time (A7), and an increase in the upper age for the inclusion criteria from less than 6 years to less than 16 years (A10). The original planned sample sizes and the sample size re-estimation results appear in A10 and are reflected in *italics*.

A summary of changes to planned analyses for the Final clinical study report (CSR) is described in the Summary of Changes Section which immediately follows below. These changes do not appear in the body of the SAP 5.0, as they were determined after the implementation of Protocol Amendment 10. These changes include those that were implemented for either of the 2 Interim CSRs (dated 07 November 2013 and 11 April 2016), which will also be applicable for the final study report. In addition, clarification is provided regarding additional changes to analyses planned for the final study report, as a result of recent communications with the Food and Drug Administration (FDA), dated 28 January 2016 and 27 January 2017.

Two additional appendices have been added to support this SAP:

Appendix B provides a summary of changes in the conduct of the study, as per the ten protocol amendments and is included for background information.

Appendix C provides for reference the Summary of Changes to Planned Analyses implemented for both Interim clinical study reports (from CSR Section 9.8.2 in each report). Some of these changes are also relevant to the Final CSR and are referred to in the Summary of Changes Section which immediately follows below.

SUMMARY OF CHANGES TO PLANNED ANALYSES FOR THE FINAL CSR.

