1.3. Design

This 2-segment study will be conducted as a multicenter, open-label, stratified, randomized evaluation of moroctocog alfa (AF-CC) in approximately 72 pediatric subjects (<16 years of age) with moderately severe to severe hemophilia A.

For segment 1, all subjects will use moroctocog alfa (AF-CC) in 1 of 2 treatment settings: on-demand (OD) therapy for 6 months (OD cohort) or prophylaxis for a 12-month period (RP cohort). Subjects who practice prophylaxis will be randomized to one of two regimens. The two prophylaxis treatment regimens, each delivering approximately 90 IU/kg/week, but differing in dosing schedule, will be:

A: 45 ± 5 IU/kg, administered twice a week

B: 25 ± 5 IU/kg, administered every other day

For segment 2, all subjects will use moroctocog alfa (AF-CC) for a 12-month period of prophylaxis treatment. Subjects who practiced on-demand therapy during segment 1 will practice prophylactic regimen B, defined above. Subjects who practiced prophylaxis during segment 1 will crossover to the other prophylactic treatment. A subset of subjects will participate in assessments for moroctocog alfa (AF-CC) PK characterization. This subset of subjects will undergo a baseline PK assessment, receiving a single open-label dose of moroctocog alfa (AF-CC) (50 \pm 5 IU/kg) with blood sampled for FVIII activity measurements before and at 0.5, 8, 24, 28 (optional), and 32 hours after the infusion.

Subjects on on-demand therapy for segment 1: Subjects who practice on-demand therapy at the time of the screening visit may continue to practice on-demand therapy with moroctocog alfa (AF-CC) in segment 1 (6-month period). These subjects will then practice prophylaxis regimen B for their 12-month period (segment 2) of treatment.

Subjects on prophylaxis treatment for segment 1: Subjects who are not assigned to the ondemand cohort in segment 1 will practice prophylaxis with moroctocog alfa (AF-CC) for both segments of the study and will be randomized in a 1:1 ratio to 1 of 2 treatment sequences (AB or BA) for a crossover evaluation of moroctocog alfa (AF-CC). Thus, subjects who practiced prophylaxis regimen A during segment 1 will crossover to prophylactic regimen B in segment 2 and vice versa. Randomization of these subjects will also be stratified by hemophilia A severity: FVIII activity <1% or 1-2% (central laboratory screening result).

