 - Revised SAE Reporting timeframe from 1 business day to within 24 hours of awareness of the event by the investigator, or if the AE is fatal or life-threatening the notification to Pfizer must be made immediately.
 - 28 Day Follow-up: SAEs are to be reported to the Drug Safety Unit through 28 calendar days after the last administration of the investigative product.
 - Discontinued use of legacy Wyeth Form 7443. The new consolidated Pfizer SAE Report Form will be used.
 - Discontinued use of legacy Wyeth Medication Error Incident Report Form (Form 15701). Instead medication errors are reported to the site monitor.
 - Some specific legacy Wyeth safety elements were maintained, such as the definitions for hemophilia events, events of special interest/circumstance, overdose definitions and actions, and medication error definitions and actions.
- Added an additional potential reason for a subject's discontinuation from the study ("if the investigator believes it is not in the subject's best interest to continue participating in the study").

Amendment 7 (dated 31 August 2011) implemented the following changes:

• Abbreviations and definitions (FVIII replacement, treatment groups, treatment regimens, treatment phases and washout) were updated.

- Clarification of 2 study cohorts: 1 OD and 1 RP, with differing study schedules and durations of study, and statistical analysis requirements. Segment 1 for the OD cohort was shortened to 6 months duration from 12 months. Segment 2 for the OD cohort and Segments 1 and 2 for the RP cohort remained at 12 months duration.
- Revised duration of study from 5.5 years to 8 years (or 98 months) due to enrollment projections.
- Updating of background information such as marketing status and PK experience.
- Removal of all references to PK recovery assessment.
- Change to exclusion criterion regarding surgery to allow planned minor surgery (and commensurate changes to permitted concomitant treatment and surgery sections).
- Addition of extra Study Procedures section to reflect the change in study cohorts.
- Change in PK part of study: Reduction in number of subjects required and reduction in number of samples required from each subject (optional 28 hour blood draw and removal of collection of an archive plasma sample) to reduce burden on the subject.
- Clarification that the moroctocog alfa (AF-CC) used in the study is a study drug, not a commercial product.

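### The primary-endpoint ABR rule for on-demand subjects uses visit 11 and visit 19 as segment ends, which does not fit the shortened 6-month on-demand segment or the 18-month schedule ending at visit 15

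*SAP*

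**What the plan says.** SAP 3.3.1.1 derives ABR as bleeds divided by days on the regimen over 365.25. SAP 3.3.1 limits this analysis to OD subjects. The two windows are:

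- Segment 1: "For segment 1 (on-demand treatment), days on treatment regimen for this calculation is defined as (date of visit 11" minus the date of visit 2, plus 1.
- Segment 2: "For segment 2 (prophylaxis), days on treatment regimen for this calculation is defined as (date of visit 19" minus the date of visit 11.

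SAP 3.3.2.1 gives the same windows for the RP cohort. There they are right: Protocol 15.1.8 places visit 11 at month 12, and Protocol 14.1 says the treatment phase "ends at the Final Study Visit (ie, visit 19, month 24 for RP subjects".

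The length of OD segment 1 is stated differently elsewhere in current text:

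- SAP Overview: "Major updates include a shortened duration for Segment 1 for the on-demand (OD) cohort to 6 months duration from 12 months".
- SAP 1.3: "on-demand (OD) therapy for 6 months (OD cohort) or prophylaxis for a 12-month period (RP cohort".
- Protocol 9.4: "A cohort of subjects was enrolled who practiced on-demand therapy for a 6-month period during segment 1, then switched to prophylaxis".
- Protocol 4, definition of the treatment phase: it "ends at the Final Study Visit (visit 15, month 18 or visit 19, month 24, depending on the cohort into which the subject is enrolled".

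Protocol 11.2 gives OD participation as about 20 or 26 months, so some OD subjects may have had a 12-month segment 1. The number on each schedule is not given.

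**The concern.** The visit numbers in SAP 3.3.1.1 match a 12-month segment 1, but the same SAP says OD segment 1 now lasts 6 months. For an OD subject on the 6-month schedule, two things go wrong:

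- He has no visit 19, so his segment 2 denominator is undefined.
- If visit 11 falls at month 12, his first six months of prophylaxis sit inside the window labelled on-demand.

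The rule produces the primary endpoint. Anyone programming it must choose a boundary that differs from the written one, and the choice affects the estimate. The study is open-label, and OD bleed rates had already been analysed for the second interim report, so this choice should not be left undocumented.

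**Working it through.** **Inputs.** SAP 1.4.1: planned mean change 4.75 bleeds/year, SD 7, on-demand ABR 11.85 in the earlier study, 18 evaluable subjects, 80% power, two-sided alpha 0.05, paired t-test. The implied prophylaxis ABR is 11.85 − 4.75 = 7.10. Visit months (7 = month 6, 11 = month 12, 15 = month 18) come from the RP schedule in Protocol 15.1.7, 15.1.8 and 15.1.10.

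**Plan's own figure.** n = ((1.96 + 0.842) × 7 / 4.75)² = 17.05, rounded up to 18. Allowing 25% attrition, 18/0.75 = 24. The stated 18 and 24 are reproduced. Exact noncentral-t power at n = 18 is 77.4%. The sample size is not in dispute; this only confirms the inputs.

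**Windows for a subject on the 18-month schedule** (on-demand months 0–6, prophylaxis months 6–18):

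| | Segment 1 | Segment 2 | Difference |
|---|---|---|---|
| Windows matching treatment | 11.85 | 7.10 | 4.75 |
| Boundary at visit 11, end at visit 15, bleeds counted by date | (11.85 + 7.10)/2 = 9.475 | 7.10 | 2.375 |
| Bleeds counted by actual treatment, divided by those same day counts | 5.925/1 = 5.93 | 7.10/0.5 = 14.2 | −8.28 |

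The third row reverses the direction of the result. The figures below follow the second row.

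**Mixed schedules.** Let p be the share of OD subjects on the 6-month schedule (not stated, range 0 to 1).

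- Mean difference = 4.75 × (1 − p/2): 4.75 at p = 0, 3.56 at p = 0.5, 2.375 at p = 1.
- Observed ratio for true ratio r = r / [(1 − p) + p(1 + r)/2]. For r = 0.50 this is 0.57 at p = 0.5 and 0.67 at p = 1.
- True ratio that would read 0.50 = (0.5 − 0.25p)/(1 − 0.25p): 0.43 at p = 0.5 and 0.33 at p = 1. This bears on Item 3 of the Summary of Changes, which asks for an upper bound of at most 0.5.

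**Power (paired t, two-sided 0.05, noncentral t).** The result depends on what happens to the SD when the windows are wrong:

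| Case | Difference | SD | n = 18 | n = 8 |
|---|---|---|---|---|
| Correct windows | 4.75 | 7 | 77% | 38% |
| p = 1, SD unchanged | 2.375 | 7 | 27% | 13% |
| p = 1, Poisson counting noise | 2.375 | 5.31 | 43% | 20% |
| p = 1, SD halves with the mean | 2.375 | 3.5 | 77% | 38% |
| p = 0.5, SD 7 in all subjects | 3.56 | 7.10 | 52% | 23% |
| p = 0.5, SD halved in 6-month subjects | 3.56 | 5.66 | 71% | 34% |

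Poisson case, assuming SD 7 applies to the correct 6- and 12-month windows: counting noise 11.85/0.5 + 7.10/1 = 30.8, leaving 49 − 30.8 = 18.2 between subjects. On the written windows the variance is 18.2/4 + 9.475/1 + 7.10/0.5 = 28.2, so SD 5.31. The p = 0.5 SDs include the between-schedule variance 0.25 × 2.375² = 1.41: √(49 + 1.41) = 7.10 and √((49 + 12.25)/2 + 1.41) = 5.66.

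n = 18 is the planning case. n = 8 is the number with both regimens at the second interim report (SAP Appendix C).

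**Corrections elsewhere.** None of Items 1–8 of the Summary of Changes touches these windows. The last-visit rule in SAP 3.3.1.1 applies only to a subject who does not complete a segment. Even if stretched to completers it could end segment 2 at visit 15, but it would not move the boundary between segments. Item 2 changes the model that compares ABRs, not how they are derived.

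**The case against.** The strongest reply is that these are stale visit numbers with an obvious intended reading. SAP 3.3.1.1 labels segment 1 as on-demand and segment 2 as prophylaxis, and divides by days on the regimen. SAP 1.3 gives 6 months. SAP 3.2.2.1 requires per-protocol OD subjects to be exclusively on-demand in segment 1, which no 6-month subject would meet under a month-12 boundary. Anyone who finds no visit 19 would look up the actual schedule and use the switch date, which gives no bias. The second interim report did produce OD estimates by regimen.

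Much of this stands as a guide to the intended meaning, and it makes silent misanalysis less likely. It does not make the written rule correct. The rule names specific visits, and the documents do not show which boundary the interim derivation used.

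Several limits on the size also stand:

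- The OD schedule is in Amendment 9, which was not supplied. Visit 11 as month 12 for OD subjects is inferred from the RP numbering, although visit 15 at month 18 agrees with it.
- The share p is unknown, and at p = 0 nothing changes.
- Power loss may be nil.
- OD enrollment is closed and all available data will be analysed, so n = 18 is illustrative; n = 8 is an interim count.
- Under Items 2 and 3 the reported model is a linear mixed model. The paired t-test and the ratio criterion are supportive.

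The absence of a visit 19 on the 18-month schedule does not depend on the inferred month of visit 11. It follows from the protocol's own definition of the treatment phase.

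**Conclusion.** The concern holds, and the rule must be corrected. As written, SAP 3.3.1.1 cannot be executed for OD subjects on the 6-month schedule that the SAP itself describes; it remains right for OD subjects with a 12-month segment 1. If the visit 11 boundary is kept, visit 15 is substituted and bleeds are counted by date, the planned difference shrinks by a fraction p/2, at most half, and a true ratio of 0.50 reads as high as 0.67. This assumes visit 11 is month 12 and constant rates at the planning values, with p unknown. The bias is against prophylaxis, so the error cannot create a false claim of benefit. What it puts at risk is the size of the estimated effect, the supportive 0.5 ratio criterion and possibly power.

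**What to change.** Reword SAP 3.3.1.1 as follows:

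- Segment 1 runs from visit 2 to each OD subject's actual end-of-segment-1 visit, when he switches to prophylaxis.
- Segment 2 runs from that date to his Final Study Visit, whether visit 15 or visit 19.
- Bleeds and the first-month washout are assigned on the same dates as the denominators.
- The report states how many OD subjects followed each schedule.

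The RP rule in SAP 3.3.2.1 needs no change. The cost is a SAP wording change and a change to the derivation; the visit dates are already collected.

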3.3.1.2. Analysis Method

The null hypothesis is that prophylactic treatment does not reduce the ABR relative to ondemand treatment. The alternative hypothesis is that prophylactic therapy results in a reduction in ABR.

An analysis of variance (ANOVA) will be conducted to compare the mean ABR between subjects in on-demand (segment 1) and prophylaxis (segment 2) treatment regimens. The ANOVA will include factors for treatment regimen (study segment 1 or 2) and a blocking factor for hemophilia severity (<1% and [1%, 2%]). The model will also include a blocking factor for subject to ensure that the comparison of ABRs from each treatment regimen is performed on a within subject basis. The p-value for treatment regimen calculated for ABR of the ITT population will be used to test the null hypothesis; a p-value less than 0.05 will be considered statistically significant. See Summary of Changes to Planned Analyses for the Final CSR (Item 2) for further discussion.

Additionally, ABR will be presented as descriptive statistics (n, mean, SD, median, interquartile range, minimum, and maximum). ABRs will be summarized by bleed type (ie, spontaneous or traumatic), by bleed location (eg, joint, soft tissue/muscle), and by treatment (ie, segment 1, segment 2).

3.3.2. Secondary Efficacy – Bleed Rate of High Frequency and Low Frequency Prophylaxis

Only RP subjects will be included in this analysis. Each RP subject will serve as his own matched control.

3.3.2.1. Variable Definition

To assess the efficacy of routine prophylaxis, the ABR will be derived for each subject for each prophylaxis regimen by using the following formula:

ABR = number of bleeds / (Days on treatment regimen/365.25)

The number of bleeds for the ABR calculation includes all bleeds requiring treatment with a FVIII replacement product during the time on treatment. For segment 1 prophylaxis, days on treatment regimen for this calculation is defined as (date of visit 11 – date of visit 2) +1. For segment 2 prophylaxis, days on treatment regimen for this calculation is defined as (date of visit 19 – date of visit 11). If a subject does not complete a study segment, the days on treatment ends at the last study visit. The ABR will be calculated 3 ways: 1) including all data from the ITT population (all RP subjects), 2) including all data from the PR_A-PR_B population and 3) including all data from the PR_A-PR_B population except the first month of each segment (considering the first month to be a washout period and allowing for an analysis of the sensitivity of ABRs to previous therapy).

